
8. Start and end of the experiment

9.Data Security and Monitoring Program

(This paragraph cannot be deleted, if not, fill in none. According to the requirements of the Ministry of Health's Measures for Ethical Review of Biomedical Research Involving Human Beings (2016), all research projects are required to have a data security and monitoring plan, and this item is one of the criteria for the ethics committee to review the project, please describe it specifically according to the requirements.)

(1) Overview of data management methods

1.Data are traceable. All clinical trial data correspond to specific subjects and investigators, and all modifications to the data are recorded in detail to create a series of traceable verification traces.

2.Correctness of data. The correctness of data mainly includes the authenticity and accuracy of data, all clinical trial data reflect the actual situation of the study truthfully without any falsification, fiction and tampering; the accuracy is reflected in the verifiable data sources, i.e. CRF, study records and entered data should be consistent with the data obtained from the actual study.

3.Data completeness. Study data were collected completely for each subject, and missing data due to special reasons were stated as to why they were missing.

4.Logical reasonableness of the data. To determine whether the data are logically unreasonable from a clinical perspective.

5.Timeliness of data. The data are observed and completed in a timely manner at the specified time points in the clinical trial.

(2) Adverse events and serious adverse events are reported and collected.

Reporting principles: 1. Report only adverse events related to the study drug 2. Complete the Spontaneous Adverse Event Report Form for all related adverse events (serious and non-serious)

The following information should also be included to determine if the event is related, possibly related, or potentially related to the drug. Determination of event-drug relevance includes: 1. reasonable temporal sequence 2. dose-response relationship 3. pharmacology 4. discontinuation of dosing and/or positive re-dosing.

Classification of the severity of drug-related adverse events:

Mild	The symptoms do not alter the patient's normal function.
Moderate	The symptoms result in some degree of functional impairment, but are not damaging, uncomfortable, or embarrassing.
Severe	The symptoms are definitely detrimental to health, with significant

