functional impairment or incapacity.

3) Medical safety measures

1. Collect information, focus on prevention. Supervise the department to report the risk information of clinical medical research in a timely manner, so that the information monitoring is in place and the risk prevention is effective.

2. Early warning, timely disposal. The department strengthens the monitoring of risks, regularly monitors and inspects, and once problems are found, reports them to the department head in a timely manner and takes decisive measures to control and resolve the risks in a timely manner, prevent the expansion and spread of risks, and minimize them.

3. We regularly assess risks and propose corrective measures to prevent them.

4. Before clinical research begins, the investigator must provide the subject with information about the treatment and the subject's rights and obligations, so that the subject fully understands and agrees to it, and signs an "informed consent" before the clinical research experiment can begin.

If one of the following situations occurs, the emergency handling procedures should be started immediately to stop the scientific clinical medical research and report to the Science and Education Section.

1. The research clinical medical research in the technical staff or key equipment, facilities and other auxiliary conditions change, can not properly carry out clinical research or may bring uncertain consequences.

2. The occurrence of serious adverse consequences directly related to the research clinical medical study.

3. The ethical flaws in this research-based clinical medical study.

4. The medical quality and medical safety risks associated with this research-based clinical medical study.

5. The clinical application of this research-based clinical medical study is inexact.

4) Communication with ethics committee and higher pharmacovigilance department

1. The research protocol needs to be developed and submitted to the Medical Ethics Committee for approval prior to the start of the project.

2. The project research should be filed with the higher drug regulatory authorities in a timely manner, and actively accept the guidance and supervision of the higher drug regulatory authorities.

5) Internal analysis plan for data

1. Data Collection

Information about patients who met the enrollment criteria and data from laboratory-related tests

were collected.

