Glomerular filtration rate	pcs							
Swollen number of 28 joints	pcs							
DAS28-ESR score	score							
Ultrasound of joints								

14. Adverse reaction record form

No adverse events have occurred	 yes  no
Name of undesirable events	
Start date of occurrence	____ Year ____ month ____ day
Dosing time and dosage	____ year ____ month ____ day ____ mg
Severity*	 Mild  Moderate  Severe
Whether to take	 yes  no

measures	
Relationship to study drugs	 Definitely related  Likely related  Possibly related  Possibly unrelated  Definitely not related
Outcome of adverse events that occurred	 Still exists  Eased  No idea Relief Date _____ year _____ month _____ day
Whether the patient withdrew from the trial because of the adverse event	 yes  no

Severity*: mild (no treatment, no discontinuation), moderate (discontinuation, no treatment), severe (discontinuation, control treatment)

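### The labels mild, moderate and severe have two conflicting definitions, in section 9(2) and in the section 14 form footnote, and the footnote has no grade for an event treated without stopping the drug

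*Protocol*

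**What the plan says.** Section 9(2) of the protocol contains a three-row table headed "Classification of the severity of drug-related adverse events". Mild reads "The symptoms do not alter the patient's normal function". Moderate reads "The symptoms result in some degree of functional impairment, but are not damaging, uncomfortable, or embarrassing". Severe begins "The symptoms are definitely detrimental to health, with significant" and ends, after a page break, "functional impairment or incapacity". All three rows describe what the event did to the patient. None mentions treatment or stopping the drug.

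The adverse reaction record form in section 14 has a severity field with the same three labels. An asterisk ties that field to a footnote: "mild (no treatment, no discontinuation), moderate (discontinuation, no treatment), severe (discontinuation, control treatment". All three of these definitions describe what was done about the event. None mentions function or harm.

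The form also asks whether measures were taken, without saying which, and whether the patient left the trial because of the event. It has no separate field for drug discontinuation or for treatment given.

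**The concern.** A severity grade can be used only if the label means the same thing each time it is recorded. Here one scale measures the effect on the patient and the other measures the clinical response to it, yet both carry the same names. A reader who sees severe in the data cannot tell whether the patient was incapacitated or whether the drug was stopped and treatment given.

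Safety of the combination is the second of the two purposes in section 1. Section 7 says that adverse effects are observed between the combination group, followed prospectively, and the abatacept-alone controls, whose data are collected retrospectively. Nothing in the protocol says that both groups are to be graded on the same definition. Section 9(1) also asks for agreement between case report forms, study records and entered data. One label with two meanings works against that aim.

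**Working it through.** The plan gives no figure to reproduce. The check is to set the two definitions side by side.

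**Step 1: does the footnote cover every case?** It uses two yes/no criteria, treatment and discontinuation, so there are 2 × 2 = 4 patterns.

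| Treated | Drug stopped | Footnote grade |
|---|---|---|
| No | No | Mild |
| No | Yes | Moderate |
| Yes | Yes | Severe |
| Yes | No | None |

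Three of the four patterns have a grade. An event treated while the drug is continued has none.

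**Step 2: can one event get two grades?** Four examples, read against both texts:

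| Event | Section 9(2) | Section 14 footnote |
|---|---|---|
| Significant impairment, harmful to health; not treated, drug continued | Severe | Mild |
| Normal function unchanged; drug stopped, not treated | Mild | Moderate |
| Normal function unchanged; drug stopped and treated | Mild | Severe |
| Normal function unchanged; treated, drug continued | Mild | None |

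The first and third rows are opposite extremes, and they go in opposite directions. The disagreement is therefore not a constant shift that could be corrected afterwards. Knowing the grade on one scale does not give the grade on the other.

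**Step 3: does scope separate the scales?** It does not. Section 9(2) applies to drug-related events. The relationship field on the section 14 form runs from definite, likely and possible relation to the drug through to no relation. Every related event on that form therefore falls within the scope of both definitions.

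**Step 4: is there a rule of precedence?** There is none. Neither section refers to the other, and the statistical section (section 11) does not mention severity.

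**The case against.** The strongest reply is that the grade has no stated use. Section 11 plans no summary by severity. The emergency stopping conditions in section 9 and the fourth exclusion criterion refer to serious consequences or reactions, and neither cites this scale. Section 7 says only that adverse effects are observed between groups. This stands, and it limits the weight of the point. A reader might infer that the safety comparison is biased in favour of one group. The document does not support that, because no severity comparison is planned and nothing indicates a direction.

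A second reply is that the only severity box printed in the protocol has its own definition directly beneath it, so a recorder using that form knows what to tick. This stands in part. The spontaneous report form named in section 9(2) is not shown, so it cannot be said that staff would enter two conflicting grades for one event. The footnote still leaves one pattern without a grade, however, and section 9(2) still states a different definition for the same related events.

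Two further readings are tempting and should not be pressed.

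- The wording of moderate in section 9(2) appears to leave out events that are uncomfortable but only somewhat impairing. The text shows clear signs of translation, so that phrase is too weak to rely on.
- Section 9(2) says "Adverse events and serious adverse events are reported and collected" and then "Report only adverse events related to the study drug". A reader might infer that unrelated events are lost. The section 14 form has boxes for unrelated events, so recording all events and reporting only related ones is a plausible reading, and the text does not contradict it.

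**Conclusion.** The inconsistency is real and can be read directly from the protocol. The same labels are defined by effect on the patient in one place and by action taken in another. They can differ by two grades in either direction, and one of the four action patterns has no grade on the form. This is not detail that could be left to a statistical analysis plan: both definitions are printed here, and a later plan cannot recover a grade if it is unknown which definition was applied.

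The consequence is limited to the recorded grades and whatever is later made of them. How often the scales would disagree cannot be computed, since the protocol gives no event rates or treatment patterns. The conclusion rests on reading both definitions as written and on the absence of any text that ranks them. It should be corrected, but it does not by itself undermine the efficacy comparison or the count of adverse events.

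**What to change.** Reconcile section 9(2) and the section 14 footnote to a single severity scale that gives every event a grade, and state that it applies to the prospective group and the historical controls alike. Which definition to adopt is for the sponsor and the investigator to decide.

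On the section 14 form, add one field for treatment given and one for drug discontinuation. Keep both separate from severity and from the existing trial-withdrawal question, since leaving the trial is not the same as stopping the drug.

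The cost is a wording change in two places, two extra form fields and slightly more recording per event. Section 10 requires ethics committee approval before a revised protocol is used. Any events already recorded would need to be regraded from source.

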Sei Muraoka et al. Abatacept is Efficacious in the Treatment of Older Patients with csDMARD-Refractory Rheumatoid Arthritis: A Prospective, Multicenter, Observational Study. This Japanese prospective, multicenter, observational study demonstrated that abciap is effective and safe in older RA patients with a history of csDMARDs-refractory disease. In both younger and older patients with csDMARDs-refractory RA, abciap was shown to be more effective than adding or switching to new csDMARDs.

Sae Ochi et al. Preferable outcome of Janus kinase inhibitors for a group of difficult-to-treat rheumatoid arthritis patients: from the FIRST Registry. This Japanese study compared the response to different classes of b/tsDMARDs in D2TRA and vD2TRA patients who were not responding to multiple b/tsDMARDs. The results suggest that JAK inhibitors are the preferred treatment option for this type of D2TRA.

(2) Subject selection basis

Patients diagnosed with refractory rheumatoid arthritis who meet the 2021 European League Against Rheumatism (EULAR) diagnostic criteria for refractory rheumatoid arthritis

4. Research Content

(1) Test population: patients with refractory rheumatoid arthritis

(2) Sample size: 90 D2TRA patients

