(3) Specific study: 90 D2TRA patients who were ineffective to conventional disease-modifying antirheumatic drugs and ineffective to treatment with 2 or more biological/targeted disease-modifying antirheumatic drugs and treated with Abacap combined with JAK inhibitors attending the outpatient and inpatient departments of Zhejiang Provincial People's Hospital from March 2022 to March 2024 were prospectively included as the observation group. Thirty patients with D2TRA treated with abciap alone in the outpatient and inpatient departments of Zhejiang Provincial People's Hospital from August 2020 to November 2021 were selected as the historical control group. There was no statistically significant difference between the observation group and the control group in terms of gender, age, disease duration, number of pressure pain in 28 joints, number of swelling in 28 joints, and DAS28 score ($P > 0.05$). Drugs were billed according to the maximum number of days of medical insurance (4 weeks), and changes in laboratory tests, number of pressure pains in 28 joints, number of swelling in 28 joints, and DAS28 score were observed in the Abciap combined with JAK inhibitor treatment group, and pre- and post-self comparisons were performed at 0, 4, 8, 12, 16, 20, and 24 weeks, along with changes in joint ultrasound and adverse effects. The changes in laboratory tests, number of pressure pains in 28 joints, number of swelling in 28 joints, and DAS28 scores were also retrospectively collected from the group treated with Abacap alone, and before and after self-comparison was performed at 0, 4, 8, 12, 16, 20, and 24 weeks, along with observation of changes in joint ultrasound and adverse effects. In addition, we observed the changes in laboratory tests, the number of pressure pains in 28 joints, the number of swelling in 28 joints, and the DAS28 score at 0, 4, 8, 12, 16, 20, and 24 weeks in the group treated with Abatacept combined with JAK inhibitor and the group treated with Abatacept alone, and compared them between the two groups for a statistically significant difference at $P < 0.05$. We also observed the changes in joint ultrasound and The changes of adverse reactions were also observed between the 2 groups.

5. Research Methodology:

Enrollment criteria (diagnostic criteria, inclusion criteria, exclusion criteria)

(1) Diagnostic criteria

The diagnostic criteria for D2TRA refer to the definition criteria proposed by EULAR 2021:

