No intervention factors were imposed on the study subjects in the study. Prospectively, 90 patients with D2TRA who were ineffective to conventional disease-modifying antirheumatic drugs and ineffective to treatment with 2 or more biological/targeted disease-modifying antirheumatic drugs and treated with Abacap combined with JAK inhibitors attending the outpatient and inpatient departments of Zhejiang Provincial People's Hospital from March 2022 to March 2024 were included as the observation group. Thirty patients with D2TRA treated with abciap alone in the outpatient and inpatient departments of Zhejiang Provincial People's Hospital from August 2020 to November 2021 were selected as the historical control group. There was no statistically significant difference between the observation group and the control group in terms of gender, age, disease duration, number of pressure pain in 28 joints, number of swelling in 28 joints, and DAS28 score ($P > 0.05$). The dosage was 125 mg per dose by subcutaneous injection once a week, and the dosage was 5 mg per dose by oral injection twice a day. The drug was billed according to the maximum number of days of medical insurance (4 weeks), and patients were observed for rheumatoid factor, anti-cyclic citrullinated peptide antibodies, immunoglobulins (IgG, IgA and IgM), C-reactive protein, blood sedimentation, white blood cells, platelets, ghrelin, glutamic aminotransferase, glutamic oxalacetic aminotransferase, globulin, creatinine, glomerular filtration rate, 28 joints at 4, 8, 12, 16, 20 and 24 weeks before and after drug administration number of pressure pain, number of swelling in 28 joints, joint ultrasound, change in DAS28-ESR score and adverse effects. To observe the changes in laboratory test indices, number of pressure pain in 28 joints, number of swelling in 28 joints, and DAS28 scores in the Abciap combined with JAK inhibitor treatment group, before and after self-comparison at 0, 4, 8, 12, 16, 20, and 24 weeks, as well as the changes in joint ultrasound and adverse effects. Also retrospectively collected the changes in laboratory test indices, number of pressure pain in 28 joints, number of swelling in 28 joints, and DAS28 score in the group treated with Abacap alone, and performed a before-and-after self-comparison at 0, 4, 8, 12, 16, 20, and 24 weeks, while observing the changes in joint ultrasound and adverse effects. In addition, we observed the changes in laboratory indices, the number of pressure pain in 28 joints, the number of swelling in 28 joints, and the DAS28 score between the Abciap and JAK inhibitor treatment groups at 0, 4, 8, 12, 16, 20, and 24 weeks, and compared them between the two groups. The changes in joint ultrasound and adverse effects between the two groups were also observed, so as to observe the clinical efficacy and safety of the Abciap combined with JAK inhibitor treatment group. $DAS28 \leq 2.6$ was defined as clinical remission, $2.6 < DAS28 \leq 3.2$ as low activity, $3.2 < DAS28 \leq 5.1$ as moderate activity, and $DAS28 > 5.1$ as high activity.

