including the Declaration of Helsinki ethical guidelines for human medical research and the relevant Chinese clinical research study norms and regulations. In the course of the study, if there is a need to revise this protocol, the revised protocol must be submitted to the Ethics Committee again for approval before implementation.

The Informed Consent Form for this study has been approved by the Medical Ethics Committee. If the Informed Consent Form is amended in writing, it will be sent to the Ethics Committee for approval to obtain the subject's consent again. Before the start of the study, the investigator provides patients with detailed information about the study, including the nature of the study, the purpose of the study, the possible benefits and risks, and the rights and obligations of the patients. The patient is fully informed and agrees, and signs the Informed Consent Form before the study can begin.

11. Statistical analysis plan

SPSS software was used for statistical analysis. Normality tests were performed using the Kolmogorov-Smirnov test, and measures conforming to a normal distribution were expressed as mean \pm standard deviation ($\bar{x} \pm s$), and comparisons between groups were made using the two independent samples t-test; measures not conforming to a normal distribution were described by median and interquartile spacing, i.e., median (25th percentile, 75th percentile) [M(P25,P75)], and comparisons between groups were made using the Mann-Whitney U anecdotal test Comparisons between groups were made using the Mann-Whitney U anecdotal sum test; count data were expressed as percentages, and comparisons between groups were analyzed using the chi-square test or Fisher's exact probability method, with differences considered statistically significant at $P < 0.05$.

12、 Form of publication of research results

Published 1-2 papers

13.Data Logging Form

Observed indicators		Week 0	Week 4	Week 8	Week 12	Week 16	Week 20	Week 24
Rheumatoid factor	IU/ml							
Anti-cyclic citrulli	U/ml							

nated peptide antibody								
Immunoglobulin G	g/L							
Immunoglobulin A	g/L							
Immunoglobulin M	g/L							
C-reactive protein	mg/L							
Blood sedimentation	mm/h							
Leukocytes	$\times 10^9/L$							
Blood platelets	$\times 10^9/L$							
Glutathione aminotransferase	U/L							
Glutathione transa	U/L							

minase								
Globulin	g/L							
Creatinine	umol/L							
Glomerular filtration rate	ml/min							

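### A Kolmogorov-Smirnov pre-test on the trial data chooses both the summary and the between-group test, so one outcome can be reported by different methods at different weeks

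*Protocol*

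**What the plan says.** Section 11 (Statistical analysis plan), repeated in the statistical methods row of the Program Summary, sets a two-stage rule. First stage: "Normality tests were performed using the Kolmogorov-Smirnov test, and measures conforming to a normal distribution were expressed as mean" with standard deviation. Second stage for measures judged normal: "comparisons between groups were made using the two independent samples t-test; measures not conforming to a normal distribution were described by median and interquartile spacing". For those judged non-normal, "comparisons between groups were made using the Mann-Whitney U" test. The threshold for group differences is given as "with differences considered statistically significant at $P < 0.05".

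The rule speaks of measures. It does not say whether normality is checked per group or pooled, per week or once per variable, or on raw values or changes. It gives no level for the check and does not say whether the test is corrected for an estimated mean and SD.

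The comparisons it governs are set out in section 4(3) and section 7. The observation group is "2) Sample size: 90 D2TRA patients" and the historical control is "Thirty patients with D2TRA treated with abciap alone". The groups are compared on laboratory tests, 28-joint counts and "the DAS28 score at 0, 4, 8, 12, 16, 20, and 24 weeks in the group treated with Abatacept combined with JAK inhibitor" and in the group on abatacept alone. The data form in section 13 has a separate column for each of the seven weeks. No primary outcome or primary week is named that would settle the method.

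**The concern.** The result of one test on the data selects the next test and the quantity reported. A t-test with means and a Mann-Whitney test with medians do not answer the same question. If DAS28-ESR is shown as a mean difference at some weeks and as a rank comparison at others, the 24-week course on which the efficacy claim rests is not one series of like quantities.

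Because the unit and level of the check are open, someone also has to settle them, possibly after seeing the data. The control data are collected retrospectively, which makes advance commitment more valuable.

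A further point is what the pre-test fails to examine. With 90 against 30 patients, the assumption to which the standard t-test is most exposed is equal variance, and a normality check does not address it.

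**Working it through.** The plan gives no error rate for this procedure, so there is no figure of its own to reproduce.

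**Inputs from the protocol.** Groups of 90 and 30 (section 4); seven weeks, 0 to 24 (sections 4 and 7); group comparisons at 0.05 (section 11).

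**Assumptions not in the protocol.** Two-sided tests; pre-test at 5% in each group at each week; Mann-Whitney used if either group rejects; within-patient correlation 0, 0.5 and 0.8; the same distribution in both groups and at all weeks, either normal or lognormal with log-SD 0.25, 0.4 or 1.0.

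**Step 1: chance switching with normal data, corrected test.** One week, two groups: 1 − 0.95² = 0.0975. Seven independent weeks, chance that both methods appear: 1 − 0.9025⁷ − 0.0975⁷ = 1 − 0.488 − 0.000 = 0.512.

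**Step 2: mixing over seven weeks, by simulation.** Critical distances are 0.159 (n = 30) and 0.094 (n = 90) with the Lilliefors correction, and 0.242 and 0.141 without it. There were 5,000 simulated trials per scenario; ranges run over the three correlations.

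| Shape | Corrected test | Uncorrected test |
|---|---|---|
| Normal | 48–52% | under 1% |
| Lognormal, log-SD 0.25 | 90–98% | 13–15% |
| Lognormal, log-SD 0.4 | 52–64% | 57–73% |
| Lognormal, log-SD 1.0 | 0% | about 3% |

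Mixing is commonest when the pre-test has middling power. It vanishes when the pre-test almost always or almost never rejects.

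**Step 3: type I error with equal variances.** Across the same shapes and versions (4,000 simulated trials per scenario), the two-stage procedure rejected a true null at a given week in 4.7–5.4% of cases. The t-test alone gave 4.3–5.1% and Mann-Whitney alone 4.6–5.3%. The two tests disagreed on significance in about 2% (normal) to 6% (strong skew) of null comparisons.

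**Step 4: type I error with unequal variances.** Let r be the control/observation SD ratio, with the observation SD set to 1 and normal data. The true variance of the mean difference is 1/90 + r²/30. The pooled t-test uses, on average, [(89 + 29r²)/118] × (1/90 + 1/30). The critical value on 118 degrees of freedom is 1.98.

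- r = 1.5: true 0.0861, pooled 0.0581, SE ratio √(0.0861/0.0581) = 1.217. The effective critical value is 1.98/1.217 = 1.63, a type I error of about 10%.
- r = 0.7: true 0.0274, pooled 0.0389, SE ratio 0.840. The effective critical value is 1.98/0.840 = 2.36, a type I error of about 2%.

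Simulation of the full two-stage rule (40,000 trials per ratio, corrected pre-test) gave 2.1% at r = 0.7, 3.1% at 0.8, 5.1% at 1, 7.8% at 1.25 and 10.5% at 1.5. The uncorrected version was within 0.2 percentage points. The Welch t-test gave 5.0% throughout. The corrected pre-test switched to Mann-Whitney in 9.5–9.9% of cases whatever the ratio, because it standardises each group by its own SD and cannot see a difference between the SDs.

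**The case against.** A reader might infer that the plan tests normality visit by visit, that an outcome therefore will be analysed by a mix of methods, and that chance alone drives the mix. The documents do not support this.

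- **Unit.** Section 11 refers to measures and names no unit. One decision per variable fits the text too, and mixing across weeks is then zero. The week-by-week comparisons and the layout of the data form make a weekly check a natural reading, not the stated one.
- **Certainty.** Even on the weekly reading, mixing runs from 0% to about 98%, depending on shape and on which version of the test is run. The protocol names SPSS but no version.
- **Cause.** Distributions may truly change over 24 weeks, for example if joint counts fall towards zero. A switch can then reflect a real change in shape.

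Nor does the within-group analysis ("before and after self-comparison at 0, 4, 8, 12, 16, 20, and 24 weeks") bear on this point: the pre-test rule is written for comparisons between groups.

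It can also be said that the unit and level of a normality check are details for a separate analysis plan, and that the error rate is barely affected. The first holds for the missing details taken alone. But the rule that the data choose the method is stated outright in a section headed as the statistical analysis plan, and it stays data-dependent even with one check per variable. The second holds only when the two groups have similar variances (step 4).

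**Conclusion.** The point holds in a limited form. Section 11 fixes a data-dependent choice of summary and test and leaves open how that choice is made. Applied weekly, it can give different methods for one outcome: about half of series for normal data with the corrected test, almost none with the uncorrected test, and 0% to about 98% over the shapes tried. These figures rest on a 5% pre-test level, a switch if either group rejects, and assumed shapes and correlations.

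With equal variances no inflation of type I error at a given week is shown. The harm there is inconsistent estimands and an analysis not settled in advance. Separately, the pre-test is no safeguard where the 3:1 group sizes make one useful. If the SDs differ by assumed ratios of 0.7 to 1.5, the type I error of the stated procedure is about 2% to 11%, against about 5% with an unequal-variance method. The protocol gives no SDs, so whether the real data fall in that range is unknown.

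**What to change.** In section 11 and in the matching row of the Program Summary, remove the Kolmogorov-Smirnov result as the rule that selects the analysis, and name one method per variable for all weeks:

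- **DAS28-ESR and the 28-joint counts:** mean difference between groups with 95% CI, adjusted for the week 0 value, by regression with standard errors that allow unequal variances. Week 0 itself is the baseline, so there the same method applies without the adjustment.
- **Rheumatoid factor, anti-CCP, CRP and ESR:** Mann-Whitney, with median (P25, P75).
- **Each remaining variable on the data form** (immunoglobulins, leukocytes, platelets, aminotransferases, globulin, creatinine, glomerular filtration rate): one named method, written down before the groups are compared.

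Normality plots may still be shown as description. Mixing across weeks is then impossible by construction.

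The cost is a change of wording, with no new data or patients. The downside is a small loss of efficiency where a rank test is used on a variable that proves close to normal.
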